## Version history

Version	Date	Section number	Description/Changes made
			changed
Draft 1	16.01.19		First draft
Draft 2	31.01.19		Minor changes to first draft
Draft 3	03.06.19		Minor changes to second draft
Draft 4	12.06.19		Minor changes to third draft
1.0	26.06.19		Finalisation including minor changes
1.1	01.07.19		Minor changes, ready for signature
1.2	11.11.22	5.2.3	Prespecified subgroup added
2.0	29.11.22		Final and included signatures

## Abbreviations

CEAC	cost-efficiency-acceptancy curve
EFS	Evalued for Safety Set
GP	General Practitioner
SAP	Statistical Analysis Plan
ICER	incremental cost effectiveness ratio
IEC	Independent Ethics Committee
IRB	Institutional Review Board
ITT	Intention-to-treat
PP	Per Protocol
SAP	Statistical Analysis Plan

# 1 Introduction

This Statistical Analysis Plan (SAP) is based on the study protocol version draft 2 of February 31, 2019 and follows the guideline for statistical analysis plans (Gamble, et al., 2017)

Some points of the statistical methods and of the study design are already described in the study protocol. This Statistical Analysis Plan aims to further specify the procedures and statistical methods applied during the final analysis of the study data.

## 1.1 Background and rationale

Depressive disorders belong to the most frequent and grave medical conditions. In Germany's general population approximately one in ten citizens is affected by them, means an absolute number of 5 to 6 million adults (1-year prevalence: 9.3%). Those affected lose 8.3 quality-adjusted life years on average and the health costs in Germany add up to a total 4.6 billion € per year. To cure depressive disorder as the most frequent mental disorder an uncomplicated and at the same time effective strategy is needed. This applies mainly for the primary medical care, as about every sixth patient in a general practitioner's (GP) office suffers from a depressive disorder. Roughly half of all depressive disorders are diagnosed and treated by a GP. However, depressive disorders are still not detected and adequately diagnosed in about 50% of all cases. The GET.FEEDBACK.GP intervention addresses this very problem. Showed by the preliminary study called DEPSCREEN-INFO the implementation of patient-oriented feedback additional to the depression screening can evidently improve mental health. A systematic analysis on the efficacy of depression screenings in primary medical care has never been conducted before in Germany.

## 1.2 Objectives

This trial is conducted to primarily determine the efficacy of a widely available feedback intervention after depression screening for depressive symptomology in six months as well as costs, depression severity after 1 and 12 months, diagnosis of depression (MINI), anxiety (GAD-7), somatic symptom severity (SSS-8) and quality-adjusted life years as secondary endpoints. Primary hypothesis: patient-oriented electronic depression feedback (including GP feedback) leads to a lower depression severity (PHQ-9) after 6 months compared to both GP feedback and no feedback at all. Secondary hypothesis: patient-oriented feedback after depression screening is more cost efficient after 6 months compared to both GP feedback and no feedback at all caused by a reduction of health costs (CSSRI). Furthermore, the influence

of Germany's first implementation of a depression screening on routine care of primary medical patients is evaluated.

The primary and secondary endpoints are in detail (Table 1 in the approval):

Instruments	Measurement			
	Baseline	1-month follow-up	6-months follow-up	12-months follow-up
Primary Endpoint				
Depression severity (PHQ-9)	x	x	x	x
Secondary Endpoint				
Clinical scales (Anxiety severity, GAD-7, somatic symptom severity, SSS-8, quality of life, EQ5D)	x	x	x	x
Patient knowledge and behavior regarding guideline recommendations (e.g., adherence, coping, search for information)			x	x
Health care use (e.g., doctor consultations, medication) (CSSRI)			x	x
Mini-International Neuropsychiatric Interview (MINI)		x	x	x
Patient activation (PAM13-D)			x	
Satisfaction and acceptance of screening and feedback (USE)			x	
Open questions (e.g., strategies in response to a diagnosis)				x
Medical record (i. e., diagnosis, treatment)	x		x	
Demographic information	x			

## 2 Study Methods

### 2.1 Trial design

The trial will be conducted as a multicentric, three-arm, observer-blinded, randomised control study under GP conditions. After depression screening using the PHQ-9 questionnaire eligible patients will be randomly put into one of three equally large study arms by specially programmed tablets administrated by a study nurse. Both patient-oriented plus GP feedback and feedback for the GP only after depression screening belong to the intervention whereas the no feedback arm belongs to the control group. At baseline patients directly fill in a questionnaire. The endpoints for the 1-, 6- and 12-months follow-up are collected via telephone interviews, which was already tested successfully in the preliminary study DEPSCREEN-INFO. The primary endpoint of this study is a change in the Patient health questionnaire-9 (PHQ-9) score for depression severity between baseline and the 6-months follow-up. The PHQ-9 is one of the most frequently used and best validated questionnaire for self-rating depressive conditions. It has the distinction of combining high sensitivity and specificity parameters and it is sensitive for changes considering depression treatment.

### 2.2 Randomization

A randomising sequence is created (boxes for 97 patients with probabilities for each condition derived from estimated prevalences and two test entries – 999 total boxes) not being SAP **2.0**

accessible for neither study nurse nor GP at any given point. After a patient has finished the baseline measurement, reached a PHQ-9 score higher than 9, randomisation happens electronically (allocation concealment). Patients are stratified by their depression severity (moderate and severe). The study is not cluster-randomised, as within every single GP's office each of the three conditions is realised and therefore an individual randomisation of patients is feasible.

### 2.3 Sample size

The sample size calculation is based on the results of the preliminary study called DEPSCREEN-INFO, which showed an effect of Cohen's  $d = 0.27$ . In this study a lower effect of  $d = 0.25$  for the intervention group compared to the other groups is supposed. The sample size was calculated for an ANOVA based on the F-test. Because of the closed test principle, in case of a significant result in this overall test, the pairwise comparisons can be performed without adjustment of the type-I error. To detect the underlying effect size through an F-test with a significance level of  $\alpha = 0.05$ , a power of  $1-\beta = 0.8$  and group effects 0 and 0.25 a sample size of  $n = 233$  is needed in every group (balanced design). This adds up to a total sample size for the actual enrolment of  $N = 699$  (computations were made with PASS 2008). The estimated prevalence of depressive disorders in a GP's office is 15%. 50% of all participants of the depression screening are not going to be eligible to further participate in the study as they achieve a lower PHQ-9 score than 10. Based on previous work a loss of 35% of included patients at the time of the 6-months follow-up is expected. Therefore, 1074 patients have to be included in the study in order to roughly maintain 699 patients for the primary analysis. Five study centres with each 10 GP's offices therefore have to include at least 14320 patients in the study. Thus, in every GP's office 287 patients (rounded from 286.4) will be screened on average. 30 patients will be asked to participate at each GP's office per day whereas only 15 of them consent and are eligible for the study. The total recruitment length then adds up to  $14350 / (15*5) = 192$  recruitment days if patients will be recruited simultaneously in all 5 centres. Considering weekends leads to  $192 * (7/5) = 269$  days or 39 weeks of recruitment. To take unforeseen recruitment problems into consideration the total length is extended to 12 months.

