### 2.4 Framework

GET.FEEDBACK.GP is planned to show superiority of the "patient-oriented and GP feedback" arm compared to "no feedback" or "GP feedback only" regarding the primary endpoint change in PHQ-9 score.

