# 3 Statistical Principles

## 3.1 Confidence intervals and *P* values

The level of statistical significance is 5% two-sided. Because of the closed testing principle, the pairwise comparisons of the three groups do not have to be adjusted for multiplicity if the overall test yields a significant result. Accordingly, all applicable statistical tests will be two-sided and will be performed using a 5% significance level. Analyses of secondary outcomes will be performed without adjustment for multiplicity. All confidence intervals presented will be 95% and two-sided.

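### The 80% power belongs to the overall F-test; beating both comparators, as the primary hypothesis requires, has about 64%, and section 2.4 replaces "both" with "or"

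*SAP*

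**What the plan says.** Section 1.2 of the SAP gives the primary hypothesis: patient-oriented feedback, which includes GP feedback, "leads to a lower depression severity (PHQ-9) after 6 months compared to both GP feedback and no feedback at all". This is the only text in the document labelled as the primary hypothesis.

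Section 2.4 describes what the trial is planned to show: superiority of that arm "compared to 'no feedback' or 'GP feedback only' regarding the primary endpoint change in PHQ-9 score".

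Section 2.3 sets the sample size. The assumed effect is d = 0.25 "for the intervention group compared to the other groups is supposed", and the basis is stated openly: "The sample size was calculated for an ANOVA based on the F-test". With α = 0.05, power 0.8 "and group effects 0 and 0.25 a sample size of" 233 per group follows, 699 in total. Sections 2.3, 3.1 and 5.2.1 then describe a closed test, in which the pairwise comparisons need no adjustment once the overall test is significant. None of the three says which pairwise comparisons must be significant for the primary hypothesis to count as confirmed, and none gives power for a pairwise comparison.

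**The concern.** There are two linked problems.

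- **The success rule is not fixed.** Lower severity than both comparators and superiority over one or the other are different criteria. When only one contrast is significant, the first rule calls the trial unsuccessful and the second calls it successful. As the SAP stands, that choice could be made after the results are known.
- **The powered test is not the test of the hypothesis.** Rejecting equality of three means does not show that one named arm beats two named comparators. For that, the overall test and both contrasts must be significant, and the probability of all three is lower than that of the first alone.

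What is at stake is the added value of patient feedback over GP feedback, which is half of the primary hypothesis. Under the looser rule a trial could be reported as positive without any evidence on that half.

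**Working it through.** **Inputs, all from the SAP**

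- Significance level: "The level of statistical significance is 5% two-sided" (section 3.1).
- Standardised means 0.25 (patient-oriented plus GP feedback), 0 and 0, with SD 1 (section 2.3).
- Equal allocation: "randomly put into one of three equally large study arms" (section 2.1).
- n = 233 evaluable per arm (section 2.3).
- Attrition: "a loss of 35% of included patients at the time of the 6-months follow-up is expected" (section 2.3).

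**Step 1. Reproduce the plan's figure.** The grand mean is 0.25/3 = 0.0833. The noncentrality parameter of the F-test is

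λ = n × Σ(mean − grand mean)² = 233 × 0.25² × 2/3 = 9.71, with 2 and 3 × 232 = 696 degrees of freedom.

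Power from the noncentral F distribution is 0.801 at n = 233 and 0.7996 at n = 232. The smallest n reaching 80% is therefore 233, as stated.

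**Step 2. One named pairwise comparison.** The noncentrality of the t-test is 0.25 × √(233/2) = 2.70. Two-sided power at 5% is 0.768. When the F-test must be significant first, it falls to 0.720.

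**Step 3. Both comparisons.** The two contrasts share the intervention arm, so their estimates have correlation 0.5. A bivariate normal calculation with that correlation gives 0.646. A simulation of 2,000,000 trials with pooled-variance t-tests on 696 degrees of freedom gives 0.645 without the F-test gate and 0.638 with it.

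**Step 4. Where the two rules part.**

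| Event at 233 per arm | Means 0.25 / 0 / 0 | Means 0.25 / 0.25 / 0 |
|---|---|---|
| F-test significant | 80% | 80% |
| F-test and at least one contrast ("or") | 80% | 72% |
| F-test and both contrasts ("both") | 64% | 2.5% |
| F-test and exactly one contrast | 16% | about 70% |

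Contrasts count only when they favour patient-oriented feedback. The means are listed in the order patient-oriented feedback, GP feedback, no feedback. The second column describes GP feedback alone working as well as the full intervention.

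**Step 5. What 80% power for both would take.** With the F-test gate, simulated power is 0.798 at 315 per arm and 0.805 at 320, so about 317 evaluable per arm are needed. That is 3 × 317 = 951 in total and 951/0.65 ≈ 1463 enrolled, against 699 and 1074 in the SAP. Holding n at 233 instead, the effect would have to be about 0.25 × √(317/233) = 0.29, which is above the 0.27 that section 2.3 reports from the preliminary study.

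**The case against.** The strongest reply is that section 2.3 contains no error of calculation. It names the test it powers, the figure reproduces, and it never claims 80% for both comparisons. Under the wording of section 2.4, power for a significant F-test and at least one favourable contrast is also 80%, so the 64% depends on the stricter reading. The closed procedure for three groups controls the familywise error at 5% under either reading, so no individual comparison is falsely claimed more often than planned. In the scenario where GP feedback works equally well, the 72% are correct conclusions about patient-oriented feedback against no feedback, and the scenario departs from the plan's assumed effects. Finally, section 5.2.1 analyses the endpoint in a mixed model, and the SAP gives no variance components from which its power could be derived.

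Each of these points is true, and together they define the finding: it is an inconsistency, neither a slip of arithmetic nor an inflation of type I error. They do not remove the conflict. Whether the trial has 80% or 64% power turns on one word that differs between two sections. The closed test protects each comparison, but it does not say which of them confirm the primary hypothesis. The mixed-model caveat applies equally to the plan's own 80%, which rests on the same ANOVA basis.

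**Conclusion.** The concern holds. The SAP contains two success rules for its primary hypothesis and does not choose between them. The 80% it states is the power of the overall F-test. For the hypothesis as worded in section 1.2, power at 233 per arm is about 64%, a 36% risk of failure under the plan's own effect. The two rules disagree in about one trial in six under that effect, and in about 70% of trials if GP feedback alone is equally effective.

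The power figures assume d = 0.25 against each comparator, no true difference between the comparators, 233 evaluable patients per arm, and the ANOVA and t-test setting of section 2.3. Any gain or loss from the mixed model is not counted. The contradiction between sections 1.2 and 2.4 does not depend on these assumptions.

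**What to change.** - **Section 2.4:** bring it into line with section 1.2. Success requires a significant overall test and significant month-6 contrasts in favour of patient-oriented feedback against both GP feedback and no feedback. Repeat the rule in section 5.2.1, where the contrasts are specified.
- **Reporting:** a significant result against one comparator only is reported as that comparison, and not as confirmation of the primary hypothesis.
- **Section 2.3:** state the power on the same ANOVA basis as the present calculation: overall F-test 80%; each pairwise comparison about 77% (72% after the overall test); both comparisons about 64%. Add that these figures do not account for the mixed model.

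The cost is SAP wording only, with no change in enrolment. The stated power for the primary hypothesis becomes less favourable. The rule needs to be fixed before the results are known, because it could not credibly be chosen afterwards.

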### 2.4 Framework

GET.FEEDBACK.GP is planned to show superiority of the "patient-oriented and GP feedback" arm compared to "no feedback" or "GP feedback only" regarding the primary endpoint change in PHQ-9 score.

## 2.5 Statistical interim analyses and stopping guidance

No interim analysis is planned. The trial will be stopped early if the Data Safety and Monitoring Board (DSMB) existing of the scientific advisory board sees any relation between participation or a certain trial condition and negative events (Serious adverse events, SAE). The scientific advisory board, principal investigator and co-project manager will discuss this option before deciding.

## 2.6 Timing of final analysis

The final analysis of the primary endpoint (depression severity after 6 months) will take place after the database has been reviewed for completeness and accuracy and is determined by the Steering Committee to be complete for database lock. According to our projection, this will happen after about 3 years. The results will be reported according to the CONSORT 2010 Guideline (Schulz, Altman, & Moher, 2010)

## 2.7 Timing of outcome assessments

The outcome and endpoints of each patient are found out in a 1-, 6- and 12-months follow-up after the patient's baseline recruitment via telephone interviews (see Section 1.2).

# 3 Statistical Principles

## 3.1 Confidence intervals and *P* values

The level of statistical significance is 5% two-sided. Because of the closed testing principle, the pairwise comparisons of the three groups do not have to be adjusted for multiplicity if the overall test yields a significant result. Accordingly, all applicable statistical tests will be two-sided and will be performed using a 5% significance level. Analyses of secondary outcomes will be performed without adjustment for multiplicity. All confidence intervals presented will be 95% and two-sided.

## 3.2 Adherence

As the intervention consists only of the feedback, the concept of adherence is not applicable.

## 3.3 Analysis populations

### 3.3.1 Intention to treat Population (ITT)

The primary analysis population is the ITT (intention to treat) population. The ITT population consists of all patients randomized.

### 3.3.2 Per Protocol population (PP)

The Per Protocol population includes all patients randomized who have no major protocol violation.

Major protocol violations are any unapproved changes in the research study design and/or procedures that are within the investigator's control and not in accordance with the IEC/IRB - approved protocol that may affect the participant's rights, safety or well-being, or the completeness, accuracy and reliability of the study data.

Major protocol violation includes ineligible participants who were included in the trial by mistake, and those for whom the intervention or other procedure differed from that outlined in the protocol, or failure of consent process.

### 3.3.3 Evaluated for Safety Set (EFS)

All randomized patients will be included into the Evaluated for Safety (EFS) set.

## 4 Trial Population

### 4.1 Screening data

[figure not shown]
The screening data will be collected using the PHQ-9 questionnaire which evaluates a patient's depression severity.

### 4.2 Eligibility

A sample is eligible if the individual visits a GP's office with personal contact to the GP, is 18 years old or older, is acceptably proficient in German, consents to participate in the study and is suspected to have a depressive disorder, i.e. a PHQ-9 score greater than 9.

A sample is excluded if the individual has a life threatening health status, suffers from a severe somatic or/and psychological disorder that needs urgent treatment and is not currently diagnosed or treated for depressive disorder or shows an acute suicidal tendency as assessed with PHQ-9 Item 9. In addition, the sample will be excluded if the individual suffers from severe cognitive or/and visual difficulties, is not being able to fill out questionnaires or leaves no contact details.

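### Does the ambiguous clause on current depression diagnosis or treatment in the section 4.2 exclusion list require a change to the SAP?

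*SAP*

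**What the plan says.** The inclusion part of SAP section 4.2 asks for a visit with GP contact, adult age, adequate German, consent, and that the person "is suspected to have a depressive disorder, i.e. a PHQ-9 score greater than 9". It sets no condition on current diagnosis or treatment.

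The exclusion part is one long sentence. After life-threatening illness, it names a person who "suffers from a severe somatic or/and psychological disorder that needs urgent treatment and is not currently diagnosed or treated for depressive disorder". The next item, acute suicidal tendency, follows the word *or*.

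Section 1.1 gives the motive for the trial: "However, depressive disorders are still not detected and adequately diagnosed in about 50% of all cases. The GET.FEEDBACK.GP intervention addresses this very problem".

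Three statements on analysis sets bear on the consequence:

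- Section 3.3.1: "The primary analysis population is the ITT (intention to treat) population". It consists of everyone randomised.
- Section 3.3.3: "All randomized patients will be included into the Evaluated for Safety (EFS) set".
- Section 3.3.2, on the per-protocol (PP) set: "Major protocol violation includes ineligible participants who were included in the trial by mistake". The same section defines major violations as departures that are "not in accordance with the IEC/IRB - approved protocol".

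**The concern.** A clause about patients who are *not* currently diagnosed or treated stands in a list of people to be kept out. Read quickly, it removes undetected, untreated depression, which is the problem that section 1.1 sets out to address. Read as a qualifier of the severe-disorder item, it makes exclusion for an urgent condition depend on the absence of a depression diagnosis or treatment, and the SAP does not explain why.

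If the clause decided who counts as eligible in the analysis, two programmers could build different PP sets from the same sentence. Section 1 does not help much: "This Statistical Analysis Plan (SAP) is based on the study protocol version draft 2 of February 31, 2019" names a draft with a date that does not exist, so the version that would settle the wording is not clearly identified.

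**Working it through.** **Step 1. The possible readings.** Let S be a severe disorder needing urgent treatment, and D a current diagnosis of, or treatment for, depressive disorder.

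- A, joint item: exclude if S and not D.
- B, separate exclusion: exclude if S or not D.
- C, entry condition misplaced in the exclusion list: exclude if S or D.

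| S | D | A | B | C |
|---|---|---|---|---|
| yes | yes | kept | excluded | excluded |
| yes | no | excluded | excluded | excluded |
| no | yes | kept | kept | excluded |
| no | no | kept | excluded | kept |

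All three agree only for S = yes, D = no, which is 1 of 4 cells. Any two of them differ in 2 of 4 cells. The SAP gives no numbers of patients per cell, so this counts combinations, not people.

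**Step 2. Which readings conflict with section 1.1.** Only B excludes a patient with neither a severe urgent disorder nor a current diagnosis or treatment (the last row). A and C keep that patient. The contradiction therefore needs reading B. The sentence joins the clause to the severe-disorder item by *and*, and separates the next item by *or*. Ordinary grammar gives A.

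**Step 3. What the rest of the SAP implies.**

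- Section 2.2 randomises after the baseline measurement on a PHQ-9 score above 9, with no mention of diagnosis or treatment status.
- Section 2.3 gives the screening count. Inputs: 1074 patients to include, 15% prevalence, and 50% ineligible because of a PHQ-9 score below 10. The stated figure reproduces: 1074 / (0.15 × 0.50) = 14320. There is no factor for diagnosis or treatment status.
- Had such a restriction been planned, the count would be larger. As an assumption only, let a share of 40%, 50% or 60% of otherwise eligible patients remain: 1074 / (0.15 × 0.50 × 0.40) = 35800, with 0.50 it is 28640, and with 0.60 it is 23867. None is near 14320.
- Section 5.2.3 plans a subgroup contrast that includes patients without a history of depression. This fits poorly with B, under which patients enter only if already diagnosed or treated. It is not proof, because a first episode may be under treatment.

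The missing screening factor speaks against B, and also against C. Together these points weigh most against B, but none is decisive.

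**Step 4. What would change in the analysis.**

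| Element | Depends on section 4.2? |
|---|---|
| ITT set (3.3.1) | No, all randomised |
| Safety set (3.3.3) | No, all randomised |
| Primary analysis (5.2.1) | No, all randomised by intention to treat |
| Secondary analyses (5.2.2) | No, analysed like the primary endpoint |
| PP set (3.3.2) | Only through eligibility, judged against the approved protocol |
| PP analysis | None named in section 5 |

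No patient moves in or out of the ITT or safety set under any reading. The targets of 699 analysed and 1074 included do not depend on the clause either.

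**The case for a change.** The best case for a change is that the SAP chose to restate eligibility and did so unclearly. It then defines a PP set that drops ineligible patients, so a flag programmed from section 4.2 would depend on the reading chosen. Nothing shown settles the reading outright, and one sentence is cheap to repair.

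The ambiguity stands, and it is wider than a choice between two readings, because a misplaced entry condition is also possible. It is also true that the clause would affect who may be randomised, and the 14320 to be screened, if recruitment had followed reading B or C.

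The rest does not carry. Recruitment is governed by the protocol, which is not at hand and may be clear; the SAP only summarises it. The flow diagram is not shown either. The PP flag is hypothetical, and section 3.3.2 already refers it to the approved protocol. Making the clause a criterion of its own would not be a neutral repair: it would discard the reading that grammar favours and, taken literally, produce the one that conflicts with section 1.1. The impossible protocol date is a separate clerical slip and does not make the clause harder to resolve.

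**Conclusion.** The sentence in section 4.2 is poorly drafted, but no change to the plan follows. The conflict with section 1.1 arises under only one of three readings, and not the one the grammar favours. Whichever is meant, 0 patients change in the ITT and safety sets, the primary and secondary analyses stay the same, and the plan names no PP analysis that could be affected. Rewording would make the text clearer without altering any specified result.

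This rests on three assumptions:

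- Eligibility during recruitment followed the approved protocol.
- Any PP flag, if one is ever used, is derived from that protocol as section 3.3.2 implies.
- The FAS named for the exploratory subgroups in section 5.2.3, which section 3.3 does not define, is not built by screening patients on section 4.2.

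Which criterion was intended is not judged here. If the SAP is reissued for other reasons, the sentence can be reconciled with section 1.1 and the approved protocol at the same time.
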